Although regulatory authorities approved the emergency use of AnMach as ventilators, it has been stated that healthcare professionals using these machines must be appropriately trained (Government UK, 2020; Food and Drug Administration Staff 2020). Similar statements have been issued by the manufacturers (Lauer et al. 2020; GE Healthcare, 2020; Getinge, 2020). To outline the potential risks related to the use of AnMach as ventilators, the UK MHRA issued a Medical Device Alert in early April 2020 highlighting the actions required to minimise hazards (Government UK, 2020). At the end of April 2020, NHS England and NHS Innovation published a new comprehensive clinical guidelines for use of AnMach to provide continuous invasive ventilatory support for adult patients during the coronavirus pandemic. The guidelines were long awaited and launched when the UK passed the surge. The guidelines described the major differences between AnMach and ITU ventilators as well as highlighted potential issues with ventilation using AnMach and provided advice how to deal with them (NHS England, 2020). It has been recommended that anaesthetic machines should be used in patients with the lowest critical care acuity scores and relatively good lung compliance. The guidelines also acknowledge that if a patient’s lung compliance (the extent to which the lungs will expand) deteriorates it may be necessary to transfer a patient on to ITU grade ventilator.

The most common issues with ventilating patients on AnMach, according to the NHS England guidance, are (NHS England, 2020):

1. Problems with altering the fresh gas flows (FGF) and the degree of rebreathing: the FGF should be set to avoid rebreathing and generation of excess humidity. Moreover, the amount of oxygen given to the patients depends on the FGF and the amount of rebreathing. An increase in FGF every 4 hours is recommended to help dry the internal components of the machine.
2. Need of changing soda lime for absorption of CO₂: the risk of CO₂ rebreathing occurs in case of exhaustion of soda lime activity.
3. Potential to deliver hypoxic mixture at low flows: low flows are not recommended for long term ventilation of ITU patients.

4. Absence of a pressure relief valve to limit the maximum pressure of the air flow given to the patients that put the receiver at increased risk of barotrauma.

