5. Increasing resistance to gas flow due to saturation of filters with water: water vapour is produced by CO₂ absorbers. If the water is not expelled, monitors may indicate easily overlooked flow tracing errors (prolonged expiratory phase, slurring of the expiratory capnography) and increased airway pressure may occur. Periodic drainage of water from the circuit is required which may result in an alternative means of ventilation being used.
6. Collection of water in dependent areas (part of tubes where water sits lower by gravity) of the breathing system: pressure/flow oscillations may be sensed by the ventilator as patient inspiratory effort which in turn will make a total respiratory rate greater than the set one and have a detrimental effect on patient's ventilation.
7. Lack of leak compensation in case of a leak of air flow: this may result in loss of inspiratory pressure and end-expiratory pressure and falling of the bellows (the bag where air flow goes in to be subsequently pushed into patient's lungs) resulting in inadequate ventilation. Several strategies need to be employed including manual ventilation during suctioning of secretions.
8. A 'backup mode' of ventilation is not always present: the lack of the apnea mode (if patients doesn't breathe the system starts ventilating for him) may result in prolonged apnea if patient loses respiratory drive while on spontaneous mode of ventilation.

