6.1 PRIMARY AIM

This observational study is set to evaluate the impact of using anaesthetic machines for ventilation of COVID-19 positive ITU patients admitted to the RFH 2NA and main recovery location. The study aims to identify issues with ventilation of critically ill patients on anaesthetic machines that are not described in available guidelines. Adverse events affecting patient's management and the staff experience of using anaesthetic machines are explored.

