 - These will provide more information about the progress of patients while being ventilated. There may be documentation that mentions difficulties that have arisen when ventilating or weaning ventilation in these patients as well as providing indications as to why patients have been switched to different modes of ventilation or device.
 - Physiotherapists' notes may help us to identify the AnMach patients.

3. Data recording and translation to Outcomes/Endpoints

The data for each patient will be recorded and anonymised in an encrypted Excel spread sheet and will include:

- Age, gender
- Reason for admission
- APACHE II score
- SOFA score
- Date of admission to ICU
- Date of intubation
- Was patient ventilated using AnMach?
- Number of days of ventilatory support before weaning ventilation
- Number of days spent weaning from ventilation to being successfully weaned from ventilator (extubation)
- Was patient transferred from AnMach onto conventional ICU ventilator?
- How many days following ventilation with the AnMach did the transfer happen?
- What was the indication for transferring a patient from an AnMach to the conventional ICU ventilator?
- Did the patient receive a tracheostomy?
- Adverse events possibly correlated with the use of AnMach: soda lime issues, gas flow issues, hypoxia, elevate pressure of ventilation, water need to be cleaned out of tubes, sudden respiratory rate increase, need for manual ventilation
- Organ support - number of days of
 - Use of one or more inotropic drugs or anti arrhythmic

- Renal - a need for renal replacement therapy
- Liver - correction of coagulopathy (plasma use), hypoglycaemia (glucose use), presence of hyperlactataemia (high lactate levels) related to liver failure
- Neuro - delirium
- Date of discharge from ICU or date of death
- Length of ITU stay

The above data will be used to identify quantitative values for the primary and secondary endpoints discussed in section 13.1. This will then be analysed as discussed in Section 13.0

9.1.1b - a prospective data collection

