13.1 Phase 1 ENDPOINTS

13.1.1 PRIMARY ENDPOINTS

- Proportion of patients who experienced any of the following adverse events possibly correlated with the use of AnMach: soda lime issues, gas flow issues, hypoxia, elevate pressure of ventilation, water need to be cleaned out of tubes, sudden respiratory rate increase, need for manual ventilation (frequency).
- Proportion of ventilation weaning failure while on AnMach (frequency) – This is defined as meeting one of the following criteria:
 - Lack of progress on AnMach – Defined as a failure to reduce ventilatory support for period of > 48 hours
 - Need for ventilation on an ITU grade ventilator – This will be a measured event of the transfer from AnMach to ITU-grade ventilator

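### The primary adverse-event endpoint is a closed list of seven events already covered by the guidance, so as defined it cannot show an issue the guidance does not describe

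*Protocol*

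**What the plan says.** The aim in protocol section 6.1 has two parts. The first is: "The study aims to identify issues with ventilation of critically ill patients on anaesthetic machines that are not described in available guidelines". The second is: "Adverse events affecting patient's management and the staff experience of using anaesthetic machines are explored". The study summary (3.0) gives the same aim.

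Section 13.1.1 defines the first primary endpoint as "Proportion of patients who experienced any of the following adverse events possibly correlated with the use of AnMach". Six of the named events are "soda lime issues, gas flow issues, hypoxia, elevate pressure of ventilation, water need to be cleaned out of tubes, sudden respiratory rate increase"; the seventh is need for manual ventilation. Section 9.1.1a, which lists the data to be recorded for each patient, gives the same seven under the label "Adverse events possibly correlated with the use of AnMach". Neither place has an open or residual category. Section 11.2 confirms that the data collected are those listed in section 9.

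Section 5.1 sets out eight numbered issues, introduced by "The most common issues with ventilating patients on AnMach, according to the NHS England guidance, are". The eighth begins: "A 'backup mode' of ventilation is not always present".

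**The concern.** An aim of finding what the guidance has missed needs an outcome that can register something unforeseen. This endpoint registers only events named in advance, and the names follow the guidance summary closely. If a chart records a new device problem and none of the seven events, the patient adds nothing to the numerator. If a new mechanism shows itself through a listed event such as hypoxia, the any-of proportion absorbs it without identifying it.

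The gap starts at data abstraction, so a later analysis plan cannot close it. An event that was never abstracted can be recovered only by going back to the charts.

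**Working it through.** The protocol gives no sample size, power or event rate to reproduce (13.2 states that there is no sample size calculation). The main check sets the endpoint list against the guidance summary.

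**Step 1. Map the seven events (13.1.1 and 9.1.1a) to the eight issues (5.1).**

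| Endpoint event | Guidance item | Link in the protocol's summary |
|---|---|---|
| Gas flow issues | 1 | Fresh gas flow and degree of rebreathing |
| Soda lime issues | 2 | Absorbent exhaustion and replacement |
| Hypoxia | 3 | Hypoxic mixture at low flow |
| Raised ventilation pressure | 4, 5 | No pressure relief valve; airway pressure rise from wet filters |
| Water in the tubes | 5, 6 | Drainage; pooling in dependent tubing |
| Sudden rise in respiratory rate | 6 | Oscillations sensed as patient effort |
| Need for manual ventilation | 7 | Used when leaks are not compensated |
| (none) | 8 | No backup mode, risk of prolonged apnoea |

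Events with a counterpart: 7 of 7. Guidance items with no endpoint event: 1 of 8 (item 8).

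**Step 2. Follow one patient through the definition.** Suppose the only problem in the chart is a device fault outside the list. Section 9.1.1a has no adverse-event field for it, and 13.1.1 scores the patient as having none of the seven events. The contribution to the numerator is 0, however common the fault is.

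**Step 3. Look at the other places where an unforeseen issue could appear.**

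- Datix review (9.1.1a, Option II): open as to type, but limited to serious incidents and with no data field or endpoint attached.
- Free-text nursing notes and daily review sheets (9.1.1a): read by the team, but no listed adverse-event field stores an unlisted event.
- Indication for transfer to an ITU ventilator (9.1.1a, 13.1.2): a recorded secondary endpoint with no preset categories, for transferred patients only.
- Lack of progress over 48 hours (second primary endpoint, 13.1.1): neutral as to cause, so it flags a patient without identifying a problem.
- Survey and interviews (9.2.1, 13.3): the survey question on problems is open and the thematic analysis is meant to bring out unexpected findings. The stated Phase 2 endpoint (13.3.1), however, is a proportion reporting difficulty and stress.

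None of these carries a rule for deciding whether an issue is inside or outside the guidance.

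**Step 4. Illustrate what an open field could yield.** Section 3.0 caps the datasets at 15. The per-patient rate *p* of an unlisted event is my assumption, because the protocol gives none. The chance of at least one such event in *n* patients is 1 − (1 − p)^n.

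| p | n = 5 | n = 10 | n = 15 |
|---|---|---|---|
| 5% | 22.6% | 40.1% | 53.7% |
| 10% | 41.0% | 65.1% | 79.4% |
| 20% | 67.2% | 89.3% | 96.5% |
| 30% | 83.2% | 97.2% | 99.5% |

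For example, 1 − 0.90^15 = 1 − 0.206 = 0.794. These figures assume that patients are independent and that the event is charted. Under the closed list, the endpoint registers none of these events at any *p*.

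**The case against.** The strongest reply is that the endpoint should not be judged against half of the aim. Section 6.1 also sets out to explore adverse events and staff experience generally, and the research question in 6.0 asks about adverse events without requiring that they be new. Counting known hazards serves both. The search for new issues belongs to the whole mixed-methods study, and Phase 2 is well suited to it. This stands, and it confines the point to the endpoint and its data field.

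A reader might infer that Phase 1 as a whole cannot address the aim. The documents do not support that: the Datix review, the free text and the indication for transfer are all open to an unforeseen problem, as step 3 shows.

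A reader might also infer from the mapping that no counted event could ever reflect a new issue. That too goes too far. Several labels are wider than their guidance match: hypoxia is wider than a hypoxic mixture at low flow, and any need for manual ventilation is wider than its use during suctioning. A new mechanism could be counted under such a label, although the endpoint would not identify it as new. Moreover, section 5.1 lists only the most common issues, and the guidance itself was not available for this check.

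Finally, the collection forms are still to be designed (11.2), so an open field might be added anyway. That makes the change easy, but section 11.2 points to section 9 for the data collected, and section 9 has no such field.

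**Conclusion.** The point holds for the primary adverse-event endpoint and its data-collection field. All seven events have a counterpart in the protocol's guidance summary, there is no open category, and one of the eight guidance issues is unrecorded. As defined, the endpoint cannot show an issue outside the guidance, which is one part of the primary aim. The open sources in both phases could reveal such an issue, but the protocol turns none of them into a defined outcome for it.

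The conclusion rests on reading the lists in 9.1.1a and 13.1.1 as complete, and on the protocol's summary of the guidance. The analysis is descriptive, so no test or power claim is affected. The existing endpoint remains a reasonable count of known hazards and need not be replaced. Making undescribed events the sole primary endpoint would be a debatable trade-off, and the finding does not require it.

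**What to change.** Keep the existing endpoint. In sections 9.1.1a and 13.1.1:

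1. Add a free-text field for any other ventilation or device problem, and enter relevant Datix findings in it.
2. Add an item for apnoea or absence of backup ventilation.
3. Code every recorded event, including those under the seven existing labels, to guidance issue 1 to 8 or to *not described in guidance*. Check the latter against the guidance itself, since section 5.1 summarises only the commonest issues.
4. Report the number and proportion of patients with at least one event coded *not described in guidance*, and list each such event. Show the listed events by type alongside.

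The cost is two form fields, one coding column and a few lines of protocol text. The charts and notes are already to be read, and the forms are not yet designed. The drawback is that coding against the guidance needs some judgement, and with at most 15 datasets a few decisions could move the proportion noticeably: one patient is 1/15 = 6.7%. Listing each event lets readers judge those decisions for themselves.

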This involves applying the inclusion criteria listed above to patients admitted to 2NA and main recovery between the 1st April 2020 and 1st June 2020. The list of these patients will be generated using the records from the Cerner EPR Computer System where all patient locations within the hospital are updated in a 'live' fashion. This will give us an accurate picture of all the patients admitted to 2NA and main recovery during the above period thus providing a population of patients who were exposed to ventilation by AnMach. In order to identify individuals who were ventilated by AnMach while in this location, we will review the nursing charts and the physiotherapy notes which we anticipate will provide evidence for the method ventilating a particular patient in that location of the hospital

2. Review of raw data:

Following identification of study participants using the inclusion criteria (Section 8.1.1), data from their admission will be reviewed and collected. This will involve manual review of the following:

- Observation charts (when released for review). These provide quantitative data and trends can be identified to provide evidence that ventilatory support was being weaned or escalated:
 - These charts will show hour by hour trends in the level of respiratory support being delivered to the patients, including; the mode of ventilation, the delivered oxygen concentration, the pressure settings of ventilation, position of the patient (i.e. whether prone or not).
 - They also show the physiological status of the patient including their hourly observations and regular blood gas sampling, thus providing evidence about

- whether the patient was deteriorating, improving or remaining static in terms of ventilatory support.
- The chart may also provide qualitative evidence of a patient weaning from ventilation. The back of the chart provides space for the nursing staff to record information regarding the course of the day using 'free-hand'. This will provide evidence of the ventilator being used as well as the clinical direction of the patient i.e. whether weaning or not.
 - Daily review sheets filled in by ICU clinicians and physiotherapists.

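### The closed seven-item adverse-event list has no dedicated item for barotrauma or, less clearly, for raised CO2, and no field for other events, so these would not be systematically counted.

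*Protocol*

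**What the plan says.** Section 13.1.1 defines the first primary endpoint as "Proportion of patients who experienced any of the following adverse events possibly correlated with the use of AnMach", followed by "soda lime issues, gas flow issues, hypoxia, elevate pressure of ventilation, water need to be cleaned out of tubes, sudden respiratory rate increase" and, as the seventh item, need for manual ventilation. The recording list in section 9.1.1a, part 3, has one adverse-event entry with the same seven items, beginning "Adverse events possibly correlated with the use of AnMach: soda lime issues, gas flow issues, hypoxia, elevate pressure of ventilation". Neither list has an entry for other events.

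Section 5.1 sets out eight hazards taken from national guidance. On soda lime, it says the risk of CO2 "rebreathing occurs in case of exhaustion of soda lime activity". On the missing pressure relief valve, it says this may "put the receiver at increased risk of barotrauma".

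Section 9.1.1a, part 2, describes the observation charts to be read: "They also show the physiological status of the patient including their hourly observations and regular blood gas sampling". The daily clinician and physiotherapy sheets are also read, for difficulties with ventilation or weaning. Under Option II the Datix incident database is searched for serious incidents related to the machines.

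**The concern.** The research question in section 6.0 asks about the impact of ventilation on an anaesthetic machine in terms of adverse events. For two of its hazards the protocol describes a chain from a machine-side condition towards the patient, then records only the machine-side condition: soda lime problems, but not raised CO2; high ventilation pressure, but not barotrauma. The people abstracting the data will have the blood gases and daily notes in front of them, but no column in which to enter either finding.

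What is at stake is how the Phase 1 results can be read. A raised ventilation pressure with no injury and a documented barotrauma could enter the primary endpoint as the same yes. The report would have no count, even a descriptive one, of patients in whom the named risk became harm.

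**Working it through.** The protocol has no sample size calculation, power statement or target precision for this endpoint, so there is no figure to reproduce. The check sets the hazards in section 5.1 against the items recorded.

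| Hazard in 5.1 | Nearest item in 9.1.1a and 13.1.1 | Named consequence with no item of its own |
|---|---|---|
| 1. Fresh gas flow and rebreathing | Gas flow issues; hypoxia | Rebreathing, unless coded under gas flow |
| 2. Soda lime exhaustion | Soda lime issues | CO2 rebreathing, unless coded under soda lime |
| 3. Hypoxic mixture at low flow | Hypoxia | None |
| 4. No pressure relief valve | Elevated pressure | Barotrauma |
| 5. Filters saturated with water | Water in tubes; elevated pressure | None |
| 6. Water in dependent tubing | Sudden respiratory rate increase; water in tubes | None |
| 7. No leak compensation | Need for manual ventilation | Inadequate ventilation, in part |
| 8. No backup mode | None | Prolonged apnoea |

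1. **Barotrauma.** It is absent from the adverse-event list, from the rest of the recording list and from the secondary endpoints in 13.1.2. Elevated pressure is a risk factor for it, not a record of it.

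2. **CO2.** Section 5.1 names rebreathing, which happens in the breathing circuit. Its measurable counterpart in the patient is a raised CO2 on blood gas. The gases are read, but no CO2 variable is extracted. Rebreathing could be entered under soda lime issues or gas flow issues, since both items are undefined, so this gap is less clear than the one for barotrauma.

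3. **Is the list closed?** The wording that introduces the recording list in 9.1.1a may leave room for additions. The endpoint counts only the events that follow in its list, and neither place has an open category.

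4. **Which results will be reported?** Section 9.1.1a calls Option II, in which the device cannot be identified from the charts, the more likely case. For that case section 13.2 says that only adverse-event data will be collected and given as proportions. Section 9.1.1a, on the other hand, says that its remaining sections, with the full recording list, refer to Option II. On the narrower reading, the adverse-event list is all that Phase 1 abstracts from the charts.

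5. **Precision if the items were added.** The study summary sets a maximum of 15 patient datasets. If no event were seen in 15, the exact upper 95% limit would be 1 − 0.025^(1/15) = 0.218 (two-sided) or 1 − 0.05^(1/15) = 0.181 (one-sided). This holds for any event not seen in 15 patients. It shows how little a zero count would exclude; it does not measure the size of this gap.

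**The case against.** A reader might infer that Phase 1 would stay silent about these harms even if they occurred. The documents do not support that. The Datix search is not confined to the seven items, the daily sheets are read for narrative difficulties, and the indication for transfer to an ITU ventilator is both recorded and a secondary endpoint. In Phase 2, the survey invites a description of problems and the interviews cover adverse events. None of these routes guarantees capture. Datix depends on a report having been filed and feeds no endpoint; the transfer item covers only transferred patients and may drop out under Option II. But they could bring cases to light.

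A reader might also infer that a patient with barotrauma could contribute only a pressure flag, or that a patient with raised CO2 must count as event-free. Neither follows. Hypoxia, sudden respiratory rate increase and need for manual ventilation are listed, so the list is not purely machine-side. Transfer to an ITU ventilator also counts in the second primary endpoint. Nor does the protocol name CO2 retention as a harm; it names rebreathing.

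Two further objections carry weight. The stated aim in section 6.1 is to find problems the guidelines do not already describe, and both of these come from the guidelines. That argues for an open field as well, but it does not explain the omission, because the seven existing items also trace to those hazards. Second, no extra column can establish cause: barotrauma or raised CO2 in a critically ill COVID-19 patient may have other origins. That stands, and it applies equally to hypoxia, which the list already accepts as only possibly related.

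Finally, the two lists agree with each other and section 5.1 does not promise to measure every consequence, so this is a gap in measurement and not a contradiction.

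**Conclusion.** The point holds in limited form. Barotrauma has no item of its own anywhere in Phase 1, and raised CO2 has none beyond what might be coded under two undefined items. With no category for other events, neither would be systematically captured or reported as a proportion, though single cases might emerge elsewhere.

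The gap cannot safely be left to a later analysis plan, because a variable that was never abstracted cannot be analysed. No numerical size can be given: the protocol offers no expected frequency for either event. The conclusion rests on reading the endpoint's list as exhaustive. It is a worthwhile, inexpensive improvement and does not invalidate the endpoint as defined.

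**What to change.** Add three fields to the recording list in section 9.1.1a and report each as a separate proportion under section 13.1, outside the existing seven-item composite so that its meaning does not change:

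- barotrauma documented in the daily clinician or physiotherapy sheets;
- raised CO2 on the charted blood gases, with the definition set by the study clinicians before abstraction begins;
- any other event thought to be related to the machine, as free text, which also takes Datix findings. This field serves the aim in section 6.1 most directly, and would take events such as the prolonged apnoea in hazard 8.

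State beside the results that, with at most 15 patients, no comparison planned without an amendment, and devices that may not be identifiable under Option II, these figures are descriptive and cannot be attributed to the machine.

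The cost is slightly more abstraction time and three more lines in the results table, all from sources already being reviewed. No clinical rule is changed.

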4.0 STUDY FLOW CHART

5.0 INTRODUCTION

5.1 BACKGROUND

The COVID-19 pandemic dramatically increased the demand for the ventilator beds in the United Kingdom (UK), generating, at the same time, Intensive Therapy Unit (ITU) ventilators shortages (Lauer et al., 2020). Anaesthetic machines (AnMach) have been commonly used as a solution to supplement ventilator capacity. The use of AnMach as a long-term ventilator is considered an off-label use but emergency use of these devices is justified when there is no available alternative because the benefits outweigh the risks (Government UK, 2020; Food and Drug Administration Staff 2020). This occurred at the Royal Free Hospital (RFH), London, in April and May 2020.

Modern AnMach are capable of providing mechanical ventilation to patients with respiratory failure, however they neither are ITU grade ventilators nor their use as such has been verified and validated

(GE Healthcare, 2020). Safe and effective use of AnMach as ventilators requires understanding of the differences between AnMach and ITU ventilators and their limitations in mimicking ventilation strategies (APSF/ASA, 2020).

Both machines provide air and oxygen from a wall to patients at desired ventilation settings and oxygen concentration. The AnMach have a rebreathing system where the expired air goes through a filter (soda lime, that has a limited capacity of absorption and needs replacing) that catches the carbon dioxide and the “cleaned” air goes back to the patient. To do this they need high flow volume, more than 50% of the patients’ minute volume (air volume given to patients each minute). The ITU ventilators are non-rebreathing systems so exhaled breath is dispersed to the atmosphere and a new air mix is given to patients at every breath. AnMach are designed to be full time attended because they have limited ability to generate alerts. Also, they may contain residual anaesthetic gas in the system that could interact with other patients’ medication. AnMach need testing every 24hours and need to be set ready to ventilate while ITU ventilators are ready to go as soon as the patient is connected (GE Healthcare, 2020).

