Prospective data may be suitable for collection depending on the course of the COVID-19 crisis. At present there are no patients at the Royal Free Hospital being ventilated on anaesthetic machines. However, if there is a 'second surge' in cases and the department is forced to re-expand and use anaesthetic machines for ventilation then there may be scope to develop a prospective element to data collection. Should there be patients being ventilated with anaesthetic machines in the future, we would consider a prospective cohort study to examine outcomes for patients ventilated by anaesthetic machines and request an amendment of the study protocol to HRA.

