13.1.2 SECONDARY ENDPOINTS

- Number of patients ventilated with an AnMach in the period of interest (continuous)
- Age (continuous), gender (categorical)

- Reason for admission (categorical)
- APACHE II score (continuous)
- SOFA score (continuous)
- Duration of ventilation - a measurement of the time from the start of ventilation until the first period of mechanical ventilation is complete (continuous)
- Length of ICU stay – A measure of the number of days between admission to ICU and discharge from ICU (continuous)
- Number of days of ventilatory support before weaning ventilation (patients on spontaneous breathing) (continuous)
- Number of days spent weaning from ventilation to being successfully weaned from ventilator (extubation) (continuous)
- Number of days following ventilation with the AnMach after which transfer to an ITU grade ventilator happened (continuous)
- Indication for transferring a patient from an AnMach to the conventional ITU ventilator (categorical)
- Proportion of patients receiving a tracheostomy (frequency)
- Organ support - number of days of (continuous)
 - Use of one or more inotropic drugs or anti arrhythmic
 - Renal - a need for renal replacement therapy
 - Liver - correction of coagulopathy (plasma use), hypoglycaemia (glucose use), presence of hyperlactataemia (high lactate levels) related to liver failure
 - Neuro - delirium
- Length of hospital stay - A measure of the number of days between admission to Hospital and subsequent discharge from hospital (continuous)
- Mortality at 28 days – proportion of patients who died in the study period (frequency)

▪

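### The weaning-failure primary endpoint is not tied to the start of weaning, counts transfers for any reason, and leaves deaths before either criterion as non-failures by default

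*Protocol*

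**What the plan says.** Protocol Section 13.1.1 lists the proportion with weaning failure on the anaesthetic machine as the second of two primary endpoints. The rule is disjunctive: "This is defined as meeting one of the following criteria".

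- Lack of progress: "Defined as a failure to reduce ventilatory support for period of > 48 hours".
- Need for an ITU-grade ventilator: "This will be a measured event of the transfer from AnMach to ITU-grade ventilator".

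Section 13.1.2 treats the time before weaning as a separate variable: "Number of days of ventilatory support before weaning ventilation (patients on spontaneous breathing) (continuous". It lists the days spent weaning next to it. The reason for transfer is a categorical secondary endpoint there, and the extraction list in Section 9.1.1a asks: "What was the indication for transferring a patient from an AnMach to the conventional ICU ventilator". Mortality at 28 days is a secondary endpoint, and the date of death is extracted. Death plays no part in the weaning-failure definition, and no denominator is given for it.

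Section 3.0 caps the patient datasets at 15. Sections 13.2 and 13.2.2 plan a descriptive analysis with no sample size calculation.

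**The concern.** The endpoint is named for weaning, but neither criterion requires that weaning has started. A patient held on constant or rising support for three days before any attempt to wean is counted under Section 13.1.2 as not yet weaning, and under Section 13.1.1 as having failed to wean over the same days.

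The second criterion is labelled as a need but measured as an event. A move made for a reason unrelated to the patient's lungs or to the machine would score the same as a move forced by deterioration.

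Death on the machine before either criterion is met is not a failure. If such patients stay in the denominator, they lower the proportion.

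Because the analysis is descriptive, with no comparator, the proportion is itself the result. Nothing elsewhere in the analysis would offset a misclassification.

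**Working it through.** The protocol gives no expected failure rate, power or sample size for this endpoint, so there is no figure to reproduce. The check is a literal reading of the rule, followed by simple proportions.

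**Step 1: patient courses set against the rule.**

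| Course on the anaesthetic machine | Score under 13.1.1 | What the other sections record |
|---|---|---|
| Not yet weaning, support unchanged for more than 48 h | Failure | Days before weaning (13.1.2) |
| Weaning begun, then no reduction for more than 48 h | Failure | Days spent weaning (13.1.2) |
| Transferred because lung compliance worsened (the clinical reason given in 5.1) | Failure | Indication (9.1.1a, 13.1.2) |
| Transferred for a non-clinical reason | Failure | Indication (9.1.1a, 13.1.2) |
| Died after more than 48 h without reduction, or after transfer | Failure | Date of death, mortality |
| Died within 48 h, or less than 48 h after the last reduction, without transfer | Non-failure by default | Date of death, mortality |

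Rows 1 and 2 differ in whether weaning had begun, and rows 3 and 4 in the reason for transfer. The protocol collects what is needed to separate each pair, but the endpoint does not use it.

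**Step 2: weight of one patient.** With n = 15 (the maximum in Section 3.0), one reclassified patient moves the proportion by 100/15 = 6.7 percentage points. With fewer patients the step is larger.

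**Step 3: illustration.** The patient mix is assumed and does not come from the documents. Let g be true weaning failures, a patients not yet weaning with more than 48 h of unchanged support, c non-clinical transfers and d deaths before either criterion, with no overlap. The literal rule gives (g + a + c)/15. A rule restricted to true weaning failures gives g/15, with d/15 shown on its own line.

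| g, a, c, d | Literal rule | Restricted rule | Early deaths |
|---|---|---|---|
| 3, 0, 0, 0 | 3/15 = 20.0% | 3/15 = 20.0% | 0/15 = 0% |
| 3, 2, 1, 1 | 6/15 = 40.0% | 3/15 = 20.0% | 1/15 = 6.7% |
| 3, 4, 2, 2 | 9/15 = 60.0% | 3/15 = 20.0% | 2/15 = 13.3% |
| 3, 6, 3, 2 | 12/15 = 80.0% | 3/15 = 20.0% | 2/15 = 13.3% |

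If early deaths were counted as failures instead, (g + d)/15 would be 20.0%, 26.7%, 33.3% and 33.3%. For scale, the exact (Clopper-Pearson) 95% interval for 3/15 is 4.3% to 48.1%. The 40.0% case lies inside it; the 60.0% and 80.0% cases do not. Pre-weaning patients and non-clinical transfers push the literal proportion up; early deaths left in the denominator hold it down.

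**The case against.** The strongest reply is that the labels (weaning failure, lack of progress, need for an ITU ventilator) show a narrower intent, and that the indication, the days to transfer and the two weaning durations will be reported anyway. In a descriptive series of at most 15, a reader could see the transfer reasons beside the composite, and no test or decision depends on it. This is partly right. But the operational text does not apply the narrower intent, and separate summaries do not show which patients made up the primary proportion.

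A second reply is that the endpoint may never be reported. Section 9.1.1a thinks it more likely that charts cannot be labelled by device, and Section 13.2 says only adverse events would then be collected. That stands, and it limits the importance of the point.

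A third is that death handling and the denominator are often left to an analysis plan, which may exist. That also has force; the death element is the lesser part of this point.

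Three stronger readings are tempting and are not supported:

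- A reader might infer that patients still ventilated when the surge area closed were all moved to ITU ventilators and scored as failures. Section 5.1 says that "emergency use of these devices is justified when there is no available alternative", and Section 9.1.1b that "At present there are no patients at the Royal Free Hospital being ventilated on anaesthetic machines". The first explains why the machines were used; the second is equally compatible with extubation or death. No capacity-driven transfer is reported, and the reason for transfer that the background gives is clinical.
- It does not follow that the endpoint mainly measures length of ventilation or the winding down of surge capacity.
- Deaths are not all non-failures. Those after more than 48 h without reduction, or after transfer, already count.

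**Conclusion.** The point holds as a defect in a definition that the protocol itself fixes. As written, the rule can label patients who have not begun weaning, and any patients transferred for non-clinical reasons, as weaning failures. It leaves deaths before either criterion as non-failures by default, provided those patients stay in the denominator. The first two parts need only a literal reading of Section 13.1.1 beside Sections 9.1.1a and 13.1.2.

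The size cannot be known from the documents. Each misclassified patient is worth 6.7 points at the maximum of 15. The assumed mixes give a distortion of anything from none to 60 points, the latter only under an extreme mix. The point matters only if anaesthetic-machine patients can be identified from the charts.

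**What to change.** Amend Section 13.1.1 before the charts are reviewed, so that the rule is not chosen with outcomes in view.

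1. Keep all anaesthetic-machine patients as the denominator. Restricting it to those who began weaning would drop the patients who never progressed, a selection problem of its own.
2. Report mutually exclusive outcomes: extubated on the machine; transferred for a clinical or device reason; transferred for another reason; died on the machine; no reduction for more than 48 h before weaning began; no reduction for more than 48 h after weaning began. Add a residual line so that the rows sum to the denominator.
3. State the order of precedence, because one patient can meet several of these.
4. Count as weaning failure only transfers whose recorded indication is clinical or device-related, and non-progress after the recorded start of weaning. Say how that start is read from the charts; the parenthesis on spontaneous breathing in Section 13.1.2 is not a clear definition.
5. Show the protocol's present composite alongside.

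The cost is protocol wording, slightly more tabulation and small cell counts. Ventilation mode by the hour, weaning durations, transfer indication and date of death are already to be extracted under Section 9.1.1a. No change to patient care is involved. Section 9.1.1a already foresees an amendment if charts can be labelled by device, and this wording could go into it.
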